**Interleaving stimulation improving dyskinesia in Parkinson's
disease: randomized, double-blind, controlled trial**

2022.5.20

Version 1.5

Interleaving stimulation improving dyskinesia in Parkinson's disease: randomized, double-blind, controlled trial

Study protocol

1. Background

The clinical utility of deep brain stimulation (DBS) for the treatment of Parkinson's disease (PD) has been well established; however, there are a variety of adverse events, such as dyskinesia among subthalamic nucleus (STN) DBS recipients due to varied postoperative management. The artificial electrical signals of deep brain stimulation are delivered with four parameters; contact (0~3), frequency (Hertz - Hz), amplitude (voltage or current) and pulse width (microseconds, μ s). It has recently been reported that interleaving stimulation can be used effectively to treat motor symptoms while avoiding side effects.

Dyskinesia

Levodopa-induced dyskinesias (LIDs) are motor complications of Parkinson's disease. LID is characterized by progressive motor disability and may interfere with quality of life.

STN-DBS has also been demonstrated to provoke or exacerbate dyskinesia (stimulation-induced dyskinesia, SID). Previous studies have showed that the proportion of stimulation-induced dyskinesia is as high as 50% to 75%.

Both kinds of dyskinesias have variable phenotypes, including chorea, ballism, dystonia, myoclonus, or combination of any of these movements. SIDs are easily evoked in patients with severe preoperative LIDs.

In general, reducing the dosage of levodopa can improve LIDs post-operation. However, this approach will fail when dyskinesia is the result of stimulation. Available programming, such as interleaving stimulation could improve dyskinesias post-operation.

So, this study is designed as a prospective, **randomized, double-blind, controlled** study to assess putative differences in the effect of interleaving stimulation and empirical stimulation with regards to post-operation dyskinesia control.

2. Study design

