2.1 Purpose

The primary objective is to assess putative differences in the effect of interleaving stimulation and empirical stimulation with regards to dyskinesia control.

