5.1 Sample size

According to the sample size estimation method of comparing the mean of two independent samples, 42 subjects are planned to be enrolled in this study. Increase the number of cases according to the 20% dropout rate, and finally enrolled 50 cases. In this study, the change scores of total scores of visit 5 (month 12) UPDRS IV comparation with baseline is the endpoint to use to calculate the sample size. The specific calculation method was as follows:

Use Power Analysis & Sample Size software 11 (SPSS 11) to calculate the sample size. The formula is as follows.

$$n = \text{Ceiling} \left\{ \frac{(Z_{1-\alpha} + Z_{1-\beta})^2 \sigma_d^2}{2\delta_1^2} \right\}.$$

The non-inferiority hypothesis

Primary Outcome Measures

The changes of dyskinesia scores (UPDRS IV, item 32 + item 33)

H0: interleaving stimulation - empirical stimulation < 0.5 score

H1: interleaving stimulation - empirical stimulation \geq 0.5 score

Significance level: $\alpha = 0.025$ (unilateral),

Power: $1-\beta = 0.8$,

Standard deviation of single group: SD = 1.1,

H0 is the null hypothesis, H1 is the alternative hypothesis. After subjects receiving interleaving stimulation, if the mean change scores of UPDRS IV equals or exceeds 0.5 points than that of those patients receiving empirical stimulation, then H0 will be rejected, non-inferiority conclusion can be made when comparing interleaving stimulation group with empirical stimulation group. If H0 can't be reject, the conclusion that the interleaving stimulation group is better than or equivalent to empirical stimulation group can't be reached.

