5.2 Statistical analysis

All of the statistical tests used bilateral analysis. $P \leq 0.05$ is considered to be statistically significance (excluding special conditions).

Description of quantitative indicators is used to calculate total cases, missing cases, average cases, standard deviation, minimum, maximum, median and the interquartile range.

Description of classification index is used in different groups of cases and percentage.

Full Analysis Set (FAS): this analysis includes all subjects who received any treatment and provided useful value after the baseline stage for analysis. It also includes violators of the research scheme and subjects with incomplete data who left the trial.

Per Protocol Set (PPS): this analysis includes all subjects who completed the research and complied with the scheme without any serious errors. It also includes subjects who quit the trial because of ineffective treatment.

Safety Analysis Set (SAS): this analysis set includes all subjects who enrolled in the trial, received at least one treatment and was used for safety evaluation. Safety information records from all subjects were evaluated, including adverse events and the results of lab examinations.

6. Adverse Event

6.1 definition

Adverse Event : An AE is defined as any untoward medical occurrence, regardless of its relationship to the study device (study suture) or the study procedure. An untoward medical occurrence includes any new, undesirable medical experience or worsening of a pre-existing condition, which occurs at any point from the surgery to Final Visit.

Serious Adverse Event: A Serious Adverse Event (SAE) is any AE that:

- led to a death,
- led to a serious deterioration in the health of the subject that either resulted in:
 - a congenital deformity or abnormality;
 - a life-threatening illness or injury;
 - a permanent impairment of a body structure or a body function;
 - in-patient hospitalization or prolongation of existing hospitalization;
 - medical or surgical intervention to prevent life-threatening illness or injury; or permanent impairment of a body structure or a body function.

Relationship of Adverse Events: It is the Investigator's responsibility to assess the relationship of an AE to the study procedure and study device.

The following guidelines should be used in determining the relationship of an adverse event

to the study device, study procedure, or other causality:

- NOT RELATED: The event is due to extraneous causes.

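### Section 5.1 sets the primary dyskinesia test up as non-inferiority with an unexplained 0.5 points, but the title and section 2.1 ask about a difference and the printed hypotheses do not match the label

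*Combined protocol and SAP*

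**What the plan says.** The title speaks of interleaving improving dyskinesia, and section 2.1 sets the objective as to "assess putative differences in the effect of interleaving stimulation and empirical stimulation with regards to dyskinesia control". Section 2.2 names the change in UPDRS IV items 32 + 33 as a primary outcome, with a time frame of 3 and 9 months.

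Section 5.1 puts this outcome under a non-inferiority heading and prints "H0: interleaving stimulation - empirical stimulation < 0.5 score", with the alternative at or above 0.5. It uses one-sided alpha 0.025, power 0.8 and "Standard deviation of single group: SD = 1.1". Rejection is described as a mean change that equals or exceeds the empirical group's by 0.5 points, after which a "non-inferiority conclusion can be made when comparing interleaving stimulation group with empirical stimulation group". If the null is not rejected, the plan says it cannot conclude that interleaving is better or equivalent. The sample size is based on total UPDRS IV at month 12 against baseline.

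Section 5.2 adds a general rule: "All of the statistical tests used bilateral analysis", at P ≤ 0.05, with an exemption for special conditions. It names no test for the primary outcome.

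On the control, the Background (section 1) states "STN-DBS has also been demonstrated to provoke or exacerbate dyskinesia (stimulation-induced dyskinesia, SID" and puts the proportion at 50% to 75%. It also says that lowering levodopa generally helps levodopa-induced dyskinesia but fails when stimulation is the cause. Section 3.4 calls lowering stimulation or medication useful, at some risk to parkinsonism. Neither section gives an effect size.

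**The concern.** A non-inferiority margin is normally a share of the control's known benefit that one agrees to give up. No such benefit on items 32 + 33 is quantified here, and 0.5 points is not explained. Two consequences follow, and they are distinct:

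- Non-inferiority alone never shows superiority, so it does not answer the question in the title or in section 2.1.
- Without a quantified control effect, being not much worse than the control does not show that interleaving affects dyskinesia at all.

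In addition, the label and the hypotheses disagree. A standard non-inferiority alternative, with benefit counted as positive, is a difference above -0.5. The printed one is at or above +0.5. If change means improvement, that is superiority by at least 0.5 points. If change means follow-up minus baseline on a scale where higher is worse, it says that interleaving is worse by 0.5. At stake is whether a null or slightly adverse result could be presented as a primary success.

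**Working it through.** **Inputs.** From section 5.1: SD 1.1 per group, one-sided alpha 0.025, power 0.80, 0.5 points, 42 patients before dropout, 50 after. From section 3.1: 25 per arm, 1:1. Assumed: 20 to 25 analysed per arm (50 × 0.8 = 40, so 20 per arm; 42 gives 21; no loss gives 25), a two-sample t-test, and benefit counted as positive. The documents state no true difference, so several are shown.

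**The plan's own 42.**
- The printed formula gives (1.960 + 0.842)² × 1.1² / (2 × 0.5²) = 18.99, so 19 per group, or 38.
- Its t-based form, SE = 1.1/√(2n) with 2n - 2 degrees of freedom, gives power 0.79997 at n = 20 and 0.820 at n = 21. So 21 per group, or 42, is reproduced.
- That variance is a quarter of the one for two independent groups. The two-group formula with 0.5 points gives 2 × (1.960 + 0.842)² × 1.1² / 0.5² = 75.98, so 76 per arm (77 with the t distribution).
- With the two-group variance, 21 per arm corresponds to a superiority test for 1.0 point: 1.0/0.339 and 0.5/0.170 are the same ratio.

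**Two-group quantities.** SE = 1.1 × √(2/n), and the 95% CI half-width is t(0.975; 2n - 2) × SE. Success on a confidence-limit test with boundary b and true benefit d has noncentrality (d - b)/SE. For the point-estimate rule at d = 0 the probability is 1 - Φ(0.5/SE).

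| | 20 per arm | 21 per arm | 25 per arm |
|---|---|---|---|
| SE | 0.348 | 0.339 | 0.311 |
| 95% CI half-width | 0.704 | 0.686 | 0.626 |
| Heading followed (b = -0.5): success at d = 0 | 28.8% | 30.1% | 35.0% |
| Same, d = -0.25 | 10% | 11% | 12% |
| Superiority (b = 0): success at d = 0 | 2.5% | 2.5% | 2.5% |
| Printed boundary (b = +0.5): success at d = 0 | 0.04% | 0.03% | 0.02% |
| Point estimate ≥ 0.5: success at d = 0 | 7.5% | 7.0% | 5.4% |
| Superiority power at d = 0.5 | 28.8% | 30.1% | 35.0% |
| Difference with 80% superiority power | 1.00 | 0.97 | 0.89 |

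The smallest observed advantage that succeeds with 21 per arm is 0.686 - 0.5 = 0.19 if the heading is followed, 0.69 for superiority, and 0.686 + 0.5 = 1.19 on the printed boundary.

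**Illustration.** Suppose an observed advantage of 0.6 points with 21 per arm. The 95% CI is 0.6 ± 0.686, or -0.09 to 1.29. That succeeds if the heading is followed and also on the point-estimate wording. It fails for superiority and on the printed +0.5 boundary.

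**The case against.** The strongest reply is that section 5.1 does not print a -0.5 margin. A reader might infer that a primary success cannot show better dyskinesia control, and that 29% to 35% is this trial's chance of a false success. The documents do not support either statement. If change is improvement, rejecting the printed null by a confidence limit would show an advantage above 0.5 points, and success at zero benefit would be 0.04% or less. The 29% to 35% belongs only to a test built as the heading says. This part of the reply stands.

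A reader might also infer that empirical stimulation has no dyskinesia benefit, so that any margin is larger than the effect to be preserved. That goes too far. Sections 1 and 3.4 describe some benefit of lowering levodopa or stimulation, and items 32 + 33 are not limited to stimulation-induced dyskinesia. The benefit is unquantified, which is not the same as zero. Nor is the missing control effect the reason why non-inferiority fails to show superiority; it never does so by itself.

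Finally, the two-sided rule in section 5.2 could give a superiority result if the 95% CI excludes 0, and one-sided 0.025 is numerically compatible with two-sided 0.05. So superiority is not ruled out. But section 5.2 names no primary test and exempts special conditions, section 5.1 holds the only stated decision rule, and no step from non-inferiority to superiority is planned. The rule conflicts with section 5.1 and does not repair it.

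**Conclusion.** The point holds as a mismatch between question, label and hypotheses. The title and section 2.1 ask about a difference; section 5.1 permits only a non-inferiority conclusion, with 0.5 points unexplained and no quantified control effect; and its printed hypotheses say something else again. Depending on the reading, zero true benefit succeeds in about 29% to 35%, 5% to 8%, or 0.02% to 0.04% of trials. On the labelled reading, interleaving that is truly 0.25 points worse succeeds in 10% to 12%. A non-inferiority success would not by itself support the claim in the title.

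These figures assume SD 1.1, 20 to 25 analysed per arm and benefit counted as positive. Whether SD 1.1 describes items 32 + 33 is unclear, because section 5.1 sizes on total UPDRS IV at month 12. The choice among the readings has to be settled before any data are seen.

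**What to change.** In section 5.1, replace the non-inferiority hypotheses and conclusion for items 32 + 33 with one superiority test:

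- **Outcome:** change at month 9, the end of the randomised period, with positive values meaning reduction and one named reference visit. Section 5.1 uses baseline, while section 2.2 lists 3 and 9 months, so the plan must choose.
- **Hypotheses:** H0, mean reduction (interleaving) - mean reduction (empirical) = 0; H1, not equal to 0; two-sided alpha 0.05, in line with section 5.2.
- **Conclusion:** claim that interleaving improves dyskinesia only if the 95% CI lies wholly above 0, and drop equivalence as a conclusion.
- **Power statement:** keep 50 patients; about 80% power for a true 1.0-point difference with 40 evaluable, and about 29% to 35% for 0.5 points with 20 to 25 per arm. Say that 1.0 point is a detectable difference and not an effect planned in the documents.
- **SD:** confirm 1.1 for the month 9 change in items 32 + 33, or replace it and recompute.

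No extra patients, visits or data are needed, since month 9 already includes UPDRS IV. The change is still more than wording: the hypothesis, sizing endpoint and time point in section 5.1 all move. The stated power becomes less favourable, and non-inferiority is lost as a fallback. At 0.5 points, 80% power would take about 76 per arm (152 in total before dropout), which the plan does not provide.

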5.2 Statistical analysis

All of the statistical tests used bilateral analysis. $P \leq 0.05$ is considered to be statistically significance (excluding special conditions).

Description of quantitative indicators is used to calculate total cases, missing cases, average cases, standard deviation, minimum, maximum, median and the interquartile range.

Description of classification index is used in different groups of cases and percentage.

Full Analysis Set (FAS): this analysis includes all subjects who received any treatment and provided useful value after the baseline stage for analysis. It also includes violators of the research scheme and subjects with incomplete data who left the trial.

Per Protocol Set (PPS): this analysis includes all subjects who completed the research and complied with the scheme without any serious errors. It also includes subjects who quit the trial because of ineffective treatment.

Safety Analysis Set (SAS): this analysis set includes all subjects who enrolled in the trial, received at least one treatment and was used for safety evaluation. Safety information records from all subjects were evaluated, including adverse events and the results of lab examinations.

6. Adverse Event

6.1 definition

Adverse Event : An AE is defined as any untoward medical occurrence, regardless of its relationship to the study device (study suture) or the study procedure. An untoward medical occurrence includes any new, undesirable medical experience or worsening of a pre-existing condition, which occurs at any point from the surgery to Final Visit.

Serious Adverse Event: A Serious Adverse Event (SAE) is any AE that:

- led to a death,
- led to a serious deterioration in the health of the subject that either resulted in:
 - a congenital deformity or abnormality;
 - a life-threatening illness or injury;
 - a permanent impairment of a body structure or a body function;
 - in-patient hospitalization or prolongation of existing hospitalization;
 - medical or surgical intervention to prevent life-threatening illness or injury; or permanent impairment of a body structure or a body function.

Relationship of Adverse Events: It is the Investigator's responsibility to assess the relationship of an AE to the study procedure and study device.

The following guidelines should be used in determining the relationship of an adverse event

to the study device, study procedure, or other causality:

- NOT RELATED: The event is due to extraneous causes.
- POSSIBLY RELATED: The event is unlikely associated, but cannot be ruled out with certainty.
- PROBABLY RELATED: The event is likely associated, but another cause cannot be ruled out with certainty.
- DEFINITELY RELATED: The event is associated with a high degree of certainty; or
- UNKNOWN: The event cannot be defined by the categories listed above.

6.2 Reporting adverse event and management: The adverse event is reported from the start of signing the informed consent to the end of the study of subjects. All adverse events should be followed up, until the adverse event is resolved, stable or the study is completed. Investigator will ensure to provide the sufficient treatment for any adverse event of any subjects. The investigator will report the serious adverse events occurred in the study and the device defects that may cause serious adverse event to the regulatory authorities at every level according to the requirements of laws and regulations. Any study-device-related SAEs will be reported to Medtronic by the investigator.

7. Publication plan

The study outcome is expected to be published on the: Journal of Parkinsonism and related diseases, Brain Stimulation, J Neurosurgery, or Movement Disorders.

8. Reference

3. Odekerken VJ, van Laar T, Staal MJ, et al. Subthalamic nucleus versus globus pallidus bilateral deep brain stimulation for advanced Parkinson's disease (NSTAPS study): a randomised controlled trial. *Lancet Neurol*. 2013; 12: 37-44.
6. Zhang S, Zhou P, Jiang S, Wang W, Li P. Interleaving subthalamic nucleus deep brain

stimulation to avoid side effects while achieving satisfactory motor benefits in Parkinson disease: A report of 12 cases. *Medicine (Baltimore)*. 2016;95(49):e5575.

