2.3 Secondary Outcome Measures

The changes of scores of United Parkinson's Disease Rating Scale Part III in interleaving stimulation compared to empirical programming modes. *[Time Frame: 3 months and 9 months]*

Scores of neuropsychological Battery in interleaving stimulation compared to empirical programming modes. *[Time Frame: 3 months and 9 months]*

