3.2 Procedures

DBS devices (Medtronic, Neuromodulation, Minneapolis, USA) approved in China (Activa® RC 37086, Pocket Adapter: Model 64001 and 64002, Extension wire: 7482, DBS lead: 3387 or 3389) are implanted by use of MRI or CT fusion for targeting and microelectrode recording for target refinement, followed by intraoperative test stimulation of the DBS lead. The pulse generators were placed in a subclavicular position on the same day.

It is allowed to use existing DBS surgery equipment and is asked to physiologically refine the DBS targets based on the best medical practices. Devices implanted into patients are initially programmed (switched on) 28 ± 5 days after surgical implantation (Week 0/ Month 0).

The patients will undergo bilateral STN DBS. Management of medication is the responsibility of the investigators at each site and was not protocol driven.

[figure not shown]
Over a 3-month period, each patient's parameters of stimulation and medications for Parkinson's disease are adjusted, based on clinical need and empirical stimulation to obtain the best clinical effect, no interleaving stimulation are allowed in this period.

At Month 3, patients are settled into either condition: with the empirical stimulation parameters or with the interleaving programming.

No routine programming plan is set during month 3 to month 9, unless the patient requires adjustment of stimulation parameters due to symptoms of Parkinson's disease or adverse effects of stimulation. The stimulation mode remains unchanged during this period and records the reason and parameters of each programming.

After month 9, the programmer can adjust the stimulation mode and parameters based on clinical need. The dopaminergic therapies are maintained stable since baseline and last in the entire duration of the study.

Fig 1

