4.1 Efficacy assessments

The primary efficacy endpoints are the changes of dyskinesia scores and the changes of PDQ-39 scores in interleaving stimulation compared to empirical programming modes. *[Time Frame: 3 months and 9 months]*

The secondary endpoints include the changes of UPDRS III scores and the changes of neuropsychological Battery scores in interleaving stimulation compared to empirical programming modes. *[Time Frame: 3 months and 9 months]*

The parameters in primary and secondary endpoints are also tested at baseline (Enrollment). After DBS activation (Month 0), patients are again assessed at Month 3, Month 9 and Month 12 in off-medication/on-stimulation and on-medication/on-stimulation, as shown in table 1. We defined “on-medication” as roughly 60 min after a patient takes

antiparkinsonian medication when both the clinician and the patient indicate that the medication dose is effective.

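### Section 5.2 tests every secondary outcome at two-sided P ≤ 0.05 with no multiplicity rule or exploratory label, and sections 2.3 and 4.1 list a Month 3 comparison that cannot show an interleaving effect

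*Combined protocol and SAP*

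**What the plan says.** Section 5.2 covers every test with one rule: "All of the statistical tests used bilateral analysis", and P ≤ 0.05 "is considered to be statistically significance (excluding special conditions"). It does not say what the special conditions are. Section 5.1 gives a different form of alpha, "Significance level: $\alpha = 0.025$ (unilateral"), but only for the hypothesis used to size the trial.

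Section 2.3 names two secondary outcomes, UPDRS III and the battery. The battery entry reads "Scores of neuropsychological Battery in interleaving stimulation compared to empirical programming modes", in the plural, with no list of tests and no composite. Section 4.1 repeats both: "The secondary endpoints include the changes of UPDRS III scores and the changes of neuropsychological Battery scores". Both sections give the time frame as 3 and 9 months. Section 4.1 has patients assessed at each post-activation visit both off and on medication with stimulation on, and does not say which state supplies the UPDRS III endpoint.

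Section 3.1 gives the interleaving group empirical stimulation for its first three months. Section 3.2 says of that period "no interleaving stimulation are allowed in this period", and places the change of mode at Month 3. Table 1 marks cognitive tests at enrolment, Month 9 and Month 12, but not at Month 3.

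**The concern.** Leaving secondary outcomes unadjusted is acceptable when they are labelled exploratory. This plan gives no such label and calls each result at P ≤ 0.05 significant, whatever happens on the primary outcomes. The visit, the medication state and the battery score are all left open, so several tests can each be run at the full 5%. In a trial of 50 patients, a chance motor or cognitive difference could then be reported as a finding about interleaving.

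Month 3 is a separate problem. Up to that visit both arms receive the same mode of stimulation, yet the visit is listed as a time point for comparing interleaving with empirical programming.

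**Working it through.** **Figure to reproduce.** The plan states no family-wise error rate for the secondary outcomes. Its only figure here is the per-test level of 0.05 (section 5.2).

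**Number of tests, k.** The documents do not fix k. These counts are compatible with them:

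- k = 2: one comparison per outcome, at Month 9 or as a single change ending at Month 9, with one medication state and one battery score.
- k = 3: UPDRS III at Months 3 and 9 in one state, plus one battery score at Month 9 as Table 1 schedules. Month 9 alone with UPDRS III in both states and one battery score also gives 3.
- k = 4: two outcomes at two visits, as sections 2.3 and 4.1 read, with one state and one battery score.
- k = 5: UPDRS III in two states at two visits, plus one battery score at Month 9.
- k = 12: an assumed battery of five scores, with UPDRS III in one state, at two visits: (1 + 5) × 2. The five is purely illustrative.

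**Formulas.** For independent tests, the chance of at least one P ≤ 0.05 when no effect exists is 1 − (1 − 0.05)^k. For example, k = 2 gives 1 − 0.95² = 0.0975, and k = 4 gives 1 − 0.95⁴ = 0.1855. For tests with common correlation ρ, the chance is 1 − ∫[Φ((1.96 − √ρ·w)/√(1−ρ)) − Φ((−1.96 − √ρ·w)/√(1−ρ))]^k φ(w) dw, evaluated numerically. Simulation with 300,000 draws agrees to within about 0.001. The values of ρ are assumptions.

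| k | ρ = 0 | ρ = 0.5 | ρ = 0.8 | Ratio to 0.05 (ρ = 0.8 to 0) |
|---|---|---|---|---|
| 2 | 0.098 | 0.091 | 0.078 | 1.6 to 1.95 |
| 3 | 0.143 | 0.125 | 0.098 | 2.0 to 2.9 |
| 4 | 0.185 | 0.156 | 0.114 | 2.3 to 3.7 |
| 5 | 0.226 | 0.183 | 0.127 | 2.5 to 4.5 |
| 12 | 0.460 | 0.319 | 0.186 | 3.7 to 9.2 |

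**Month 3, sections side by side.** Under 3.1 and 3.2 neither arm may receive interleaving before Month 3. Provided the Month 3 rating is made before the change of mode, the effect of interleaving on a Month 3 between-arm comparison is zero by design. The documents do not state the order of rating and reprogramming at that visit. Allocation takes place before implantation and is known to the programming clinician (3.1), and medication is not protocol driven (3.2). Systematic differences by Month 3 are therefore possible without any interleaving.

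**Battery at Month 3.** Sections 2.3 and 4.1 require it; Table 1 does not schedule it. If the time frame means a change from Month 3 to Month 9, the battery has no scheduled Month 3 value to subtract. The conflict remains under either reading.

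**The case against.** The strongest reply is that section 5.2 sets a per-test level and never promises a 5% rate for the secondary family, so no stated figure is breached. That is correct: the defect is a missing rule. The reply adds that the time frame may mean one change from Month 3 to Month 9, with Month 3 as the pre-switch reference. With one medication state and one battery score that leaves two tests, a rate of 7.8% to 9.75%, and no separate Month 3 test. This reading is plausible and sets the lower end of the range, but the text does not choose it.

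A reader might infer that the secondary false-positive rate is 2.5 to 5 times 5%. That range needs about 3 to 5 independent tests, or 3 to 8 at correlation 0.5, and the documents give neither the number of battery scores nor a correlation. A reader might also infer that a significant Month 3 result can only be a false positive. That is too strong, because an unmasked programmer and unscripted medication could produce a real difference unrelated to interleaving.

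It is also fair to say that a fixed testing sequence is only one remedy. Gating on the primary cannot be applied as the plan stands: section 2.2 has two primary outcomes at two time points, section 5.1 sizes the trial on Month 12 total UPDRS IV, and success is not defined.

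**Conclusion.** The point holds as a missing multiplicity rule or exploratory label, together with a misplaced Month 3 comparison. With no true secondary effect, the chance of at least one significant secondary result is about 8–10% for 2 tests and 11–19% for 4, for correlations from 0.8 to 0. Testing UPDRS III in both medication states or several battery scores raises it further. These figures assume equal correlation between tests, and the count and correlation are not from the documents. No single multiplier can be stated.

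If the rating precedes the change of mode, a Month 3 between-arm difference is chance or bias and cannot support a claim for interleaving. This part does not depend on the test count. The conflict between 2.3/4.1 and Table 1 over Month 3 cognitive testing stands on the text alone. The plan should be changed, but nothing here affects the validity of the data to be collected.

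**What to change.** In 2.3, 4.1 and 5.2:

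1. Make Month 9 the only between-arm secondary comparison. Use Month 3 only as the pre-switch reference or as a description of the arms, and state that its rating is made before any change of mode.
2. Reconcile 2.3 and 4.1 with Table 1 on cognitive testing at Month 3.
3. Pre-name one medication state for Month 9 UPDRS III as the key secondary outcome. That leaves one secondary test at the 5% level.
4. Label the other medication state and all battery scores exploratory, reported as estimates with 95% confidence intervals and no significance claim.
5. Define the special conditions in 5.2 or delete the phrase.

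A fixed sequence after the primary is an option once primary success is defined.

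The cost is a few sentences, with no added patients, visits or data, unless the reconciliation adds a Month 3 cognitive assessment. The downside is that individual battery findings, including any worsening, lose the significance label; their estimates and intervals would still be reported.
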